12.2.2. Additional Efficacy parameters

An additional efficacy parameter is the injected tumor response (ITR) and bystander tumor response (BTR) rate, defined as either the number of injected or non-injected bystander tumors with confirmed CR or PR, divided by the total number of injected or bystander tumors identified at baseline. Tumor response status will be assessed using iRECIST response categories for tumors that have not been injected (as detailed in Section 18.1). Up to 9 bystander tumors will be identified at baseline and followed. Evaluation of individual bystander tumors will take place at every visit, with overall response (Complete, Partial, Stable, Progressive,

Not evaluable) adjudicated for each. BTR calculation will only include bystander tumors that are not injected at that visit.

An exploratory analysis will combine all efficacy measures (injected and bystander) to calculate an overall response rate (ORR) using iRECIST criteria, with the modification to allow more than 5 target tumors in the calculation of sum of diameters. The ORR will be based on the number of subjects with confirmed CR or PR, divided by the total number of subjects with measurable disease at baseline.

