For DCR, exact binomial 95% confidence intervals will be determined by Clopper-Pearson method. Median time to response and duration of response will be summarized for those subjects with confirmed responses, using Kaplan-Meier method; Progression free survival (PFS) will be similarly summarized. Individual tumor measurements, tumor burden and % changes in tumor burden will be listed. Changes in tumor burden will be presented graphically.

14.3.4. **Concomitant Medication**

Concomitant medications will be coded using the World Health Organization Drug Dictionary (WHODD). Concomitant medications will be summarized. Tabulation will be made with respect to the proportion of subjects taking at least 1 concomitant medication for each preferred term during the study. A listing of concomitant medications by subject will be provided.

14.3.5. **Safety**

The primary objective is to assess the safety and tolerability of multiple intratumoral doses of INT230-6 in subjects with advanced or recurrent malignancies. This will be assessed by the rate of \geq grade 3 AEs

Protocol IT-01 Version Amendment 6

attributed to study drugs (INT230-6 and others per the appropriate protocol supplement), and study procedure, and not the underlying disease.

Safety Analyses:

All recorded adverse events will be listed and tabulated by system organ class, preferred term, and coded according to version 19.1 of Medical Dictionary for Regulatory Activities (MedDRA). The incidence of adverse events will be tabulated and reviewed for potential significance and clinical importance. Vital signs and clinical laboratory test results will be listed and summarized. Any significant physical examination (PE) findings and results of clinical laboratory tests will be listed. Electrocardiogram (ECG) listings will be evaluated by the investigator and abnormalities, if present, will be listed.

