iUPD	iUPD	Yes	iUPD	Remains iUPD unless iCPD confirmed based on further increase in: 
 o previously identified T lesion iUPD ≥ 5 mm and / or o previously identified NT lesion iUPD (need not be unequivocal) and /or o size or number of new lesions previously identified
Non- iUPD/PD	Non-iUPD/PD	Yes	iUPD	Remains iUPD unless iCPD confirmed based on 
 o increase in size or number of new lesions previously identified

* Using RECIST 1.1 principles. If no PSPD occurs, RECIST 1.1 and iRECIST categories for CR, PR and SD would be the same. ** in any lesion category. *** previously identified in assessment immediately prior to this TP.

All patients will have their iBOR from the start of study treatment until the end of treatment classified as outlined below.

Table 16: iRECIST Best Overall Response (BOR)

TPR1	TPR2	TPR3	TPR4	TPR5	iBOR
iCR	iCR, iPR, iUPD, NE	iCR, iPR, iUPD, NE	iUPD	iCPD	iCR
iUPD	iPR, iSD, NE	iCR	iCR, iPR, iSD, iUPD, NE	iCR, iPR, iSD, iUPD, iCPD, NE	iCR
iUPD	iPR	iPR, iSD, iUPD, NE	iPR, iSD, iUPD, NE, iCPD	iPR, iSD, iUPD, NE, iCPD	iPR
iUPD	iSD, NE	PR	iPR, iSD, iUPD, NE	iPR, iSD, iUPD, iCPD, NE	iPR
iUPD	iSD	iSD, iUPD, NE	iSD, iUPD, iCPD, NE	iSD, iUPD, ICPD, NE	iSD
iUPD	iCPD	Anything	Anything	Anything	iCPD
iUPD	iUPD	iCPD	Anything	Anything	iCPD
iUPD	NE	NE	NE	NE	iUPD

- Table assumes a randomised study where confirmation of CR or PR is not required.
- NE = not evaluable that cycle.
- Designation “I” for BOR can be used to indicate prior iUPD to aid in data interpretation.
- For patients with non-target disease only at baseline, only CR or non-CR/non-PD can be assigned at each TPR but is not shown in the table for ease of presentation.

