Adverse Events were summarized for all reported data and by study period: a) up to and including 28 days post last dose of initial treatment.

Efficacy Analyses: The primary efficacy endpoint of disease control rate (DCR), defined as the sum of complete, partial and stable disease responses divided by the total number of subjects in the efficacy population, will be determined per criteria based on RECIST or iRECIST. DCR was tabulated overall and by subgroups of interest.

For DCR, exact binomial 95% confidence intervals will be computed using the Clopper-Pearson method. Median time to response and duration of response will be summarized for those subjects with responses, using the Kaplan-Meier method; overall survival (OS) will be similarly summarized. Individual tumor measurements, tumor burden, % changes in tumor burden, and progression free survival (PFS) will be listed.

Changes in overall survival will be presented graphically for all monotherapy subjects, for monotherapy subjects receiving an INT230-6 dose volume over the course of their treatment less than or \geq 40% of their incoming reported total tumor burden, with pembrolizumab, with ipilimumab and in all sarcoma types (collectively) for monotherapy and combined with ipilimumab.

Pharmacokinetic Analyses: The pharmacokinetic analyses described will be reported in a separate report. A brief summary of the results will be included in this CSR. The release kinetics of each analyte is not expected to be uniform across subjects. Sponsor shall assess the blood concentrations of the three analytes for each subject at the first cycle. Sponsor shall correlate the systemic measurement [maximum plasma drug concentration (C_{max}), area under the curve (AUC)] of the 3 analytes to measured markers of systemic toxicity [in particular renal and blood – the known toxicities of the two active agents; cisplatin (CIS) & vinblastine (VBL)]. Human plasma will be analyzed for the concentration of VBL and 8-((2-hydroxybenzoyl)amino)octanoate (sodium salt form) (SHAO) using validated LC/MS/MS methods, and for cisplatin using a validated ICP-MS method. For pharmacokinetic profiling platinum drugs, total platinum levels in subject plasma or urine are routinely determined by spectroscopy methods as a surrogate. Thus an ICP-MS method will be developed for this study to measure total platinum in human samples as a surrogate for cisplatin.

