4.3. Randomization and Blinding

This is an open-label non-randomized study.

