9.1. Additional Efficacy Analysis

Additional efficacy parameters include the duration of response (DOR), the injected tumor response (ITR), the bystander tumor response (BTR), progression free survival (PFS), and overall survival (OS). These endpoints will be summarized by treatment (see section 7 for definition of each treatment) and subgroup. Other than 1 listing reporting bystander tumors' diameter that declined over time that declined (noted below), the bystander tumor response rate (BTR) analysis will be conducted separately from the SAP from collected radiographic data.

DOR is defined as the time from first tumor assessment of CR, PR, or SD to the time of progressive disease or death due to any cause. For responders with no death or progression, DOR will be censored on the last non-PD tumor assessment or follow-up call.

The median DOR as obtained from Kaplan-Meier methods will be presented by treatment and subgroup and will include the median, 25th percentile, 75th percentile, and a 2-sided point-wise 95% confidence interval.

ITR will be based on the target tumors at the baseline visit; tumors that become target during the study will also be included in the ITR calculation at the time they are treated. The ITR is defined as the ratio of CR + PR in injected tumors / total number of injected tumors. Thus, bystander or non-target lesions dosed at later dates are not included in calculations for ITR.

The ITR will be calculated based on the maximum likelihood estimator and summarized in tables. The estimate of ITR will be accompanied by 2-sided 95% exact binomial confidence intervals as determined by the Clopper-Pearson method and assessed at each study-specified timepoint where an assessment is performed.

The BTR will follow the same definition as the ITR for bystander tumors. Note that bystander tumors that are injected on study will be included in the ITR calculation.

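### The protocol counts only confirmed CR/PR, but the SAP has no confirmation step, assesses injected-tumor response visit by visit, and declares no change from the protocol

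*SAP*

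**What the plan says.** **Protocol.** Section 12.2.2 sets the ITR and BTR numerators as "number of injected or non-injected bystander tumors with confirmed CR or PR". For ORR the same section says "The ORR will be based on the number of subjects with confirmed CR or PR". Section 14.3.3 carries this through to the time-to-event summaries: "Median time to response and duration of response will be summarized for those subjects with confirmed responses". The protocol's iRECIST appendix takes a different line for best overall response. A note under Table 16 reads "Table assumes a randomised study where confirmation of CR or PR is not required".

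**SAP.** Section 9.1 has "The ITR is defined as the ratio of CR + PR in injected tumors / total number of injected tumors" and gives BTR the same definition. Appendix 1 item 3 judges each injected tumor at a given visit, taking a PR as a volume change of at least 30% and a CR as no visible tumor. Item 4 applies that method to bystander tumors. Section 9 builds best overall response on modified RECIST 1.1 criteria and asks for no second assessment. The SAP synopsis repeats the protocol sentence on time to response and duration of response without the word on confirmation: "Median time to response and duration of response will be summarized for those subjects with responses, using the Kaplan-Meier method". Section 4.3 states "This is an open-label non-randomized study". Section 13 lists no changes from the protocol's methods.

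**The concern.** A response that need be seen only once can come from a single low measurement. With no randomised comparator, nothing offsets such false responses: they add directly to the reported rate. Requiring the response to be seen twice filters out most of them, and the protocol asks for that.

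The outputs exposed are ITR, a secondary endpoint in DEC, DEC2 and FEC (SAP Table 2), and best overall response, which is exploratory. SAP 9 says the efficacy analyses will concentrate on individual tumors, so ITR will be prominent in the report. A reader who relies on SAP 13 would take the reported rates to be the confirmed rates that the protocol promises.

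**Working it through.** **1. Protocol and SAP compared.**

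| Item | Protocol | SAP |
|---|---|---|
| ITR | confirmed (12.2.2) | any CR/PR, per visit (9.1, Appendix 1 item 3) |
| BTR | confirmed (12.2.2) | same as ITR (9.1, Appendix 1 item 4) |
| ORR | confirmed (12.2.2) | listed for DEC and DEC2 (Table 2), no numerator given |
| Time to and duration of response | confirmed responders (14.3.3) | responders (synopsis) |
| Best overall response | not confirmed (Table 16, assuming randomisation) | modified criteria, not confirmed (9) |

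The protocol does not say what interval makes a response confirmed. Its window of 4 to 8 weeks (18.1.2) is for progression only.

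**2. The plan's own precision figures.** Exact 90% Clopper-Pearson intervals with 16 subjects are 5.3 to 41.7% (3 responders), 9.0 to 48.4% (4) and 13.2 to 54.8% (5). They match Protocol 14.1 and SAP 5. Confirmation changes which responders are counted, not these intervals. As a hypothetical case, if 2 of 5 responses were not confirmed, the rate would fall from 5/16 = 31.3% to 3/16 = 18.8%, and the interval from 13.2–54.8% to 5.3–42%.

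**3. Size for an unchanged tumor.**

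Assumptions (none in the documents): log-normal error with SD *s* on each diameter, independent between diameters and visits, and one baseline shared by all visits. The values of *s* are 0.05, 0.10 and 0.15.

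- With *k* diameters in the measure, the log change from baseline has SD = s√(2k). Here k = 3 for volume from three dimensions and k = 1 for a single diameter.
- A PR needs a log change of at most ln 0.7 = −0.357.
- One visit: P₁ = Φ(−0.357 / (s√(2k))). For s = 0.10 and k = 3, the SD is 0.245, z = 1.456 and P₁ = 7.3%.
- Two consecutive visits: P₂ is the bivariate normal probability that both fall below the cut. The correlation is 0.5 because the baseline is shared.

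| Rule | Error per diameter | One visit | Two consecutive visits |
|---|---|---|---|
| 30% volume, three dimensions | 5% | 0.2% | 0.01% |
| | 10% | 7.3% | 2.1% |
| | 15% | 16.6% | 6.7% |
| 30% diameter | 5% | about 0 | about 0 |
| | 10% | 0.6% | 0.06% |
| | 15% | 4.6% | 1.1% |

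Simulation of the same model agrees within 0.2 percentage points. If volume is derived from one diameter cubed, so that the error is fully shared, the 10% row becomes 20.0% against 8.7%.

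**4. Best overall response.** Here a single qualifying visit is carried forward. At 10% error under the volume rule, the chance of at least one false PR in three visits is 16.5%. The chance of two consecutive ones within those three visits is 3.2%.

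**The case against.** Much of the opposing case stands and limits the point.

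- **ITR is a rate at each visit.** A reader might apply the 16.5% any-of-three figure to ITR, or infer that ITR rises with the number of visits. The documents do not support that: SAP 9.1 and Appendix 1 report ITR at each timepoint, so a one-off dip counts at that visit only. The any-of-three figure belongs to best response.
- **The size depends on the rule and on an assumed error.** The large figures need the 30% volume rule in Appendix 1. SAP 9 refers to RECIST 1.1 on target lesions, and on diameter the effect is small at 10% error.
- **Swelling does not create responses.** A reader might think that swelling after injection adds false PRs. The rationale for Amendment 5 reports larger volumes at the first scan, which would hide a PR.
- **The reach is narrower than three endpoints.** SAP 9.1 sends the BTR analysis outside the SAP, and Table 2 does the same for injected and bystander rates in the monotherapy cohorts, although 9.1 still defines both. For ORR the gap is by omission: the SAP states no rule, so one cannot say that it adopts unconfirmed ORR.
- **The disease control rate is not materially inflated.** An unconfirmed PR would usually become SD and still count.

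It could also be argued that Appendix 1's reference to RECIST 1.1 brings confirmation in. That fails. The same paragraph gives its own rule for a given visit, and SAP 9 says that RECIST 1.1 assessments were not collected and that modified criteria apply. Table 16 does not settle the matter either, because its waiver assumes a randomised study.

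**Conclusion.** The point holds in this limited form. The SAP omits a confirmation requirement that the protocol states for ITR, BTR, ORR, time to response and duration of response, and SAP 13 is wrong to report no change. This conclusion rests on the text alone.

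The size rests on the assumed error. At 10 to 15% per diameter under the volume rule, single-visit false PRs are about 3.5 times (7.3/2.1) to 2.5 times (16.6/6.7) as frequent as those seen at two consecutive visits. At 5% error both rates are close to zero when volume comes from three dimensions. The endpoints exposed are secondary or exploratory. The change should be made, but it does not undermine the primary safety analysis or the disease control rate.

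**What to change.** - In SAP 9, 9.1 and Appendix 1 items 3 and 4, derive ITR, BTR, ORR and best overall response on CR/PR met again at the next evaluable scheduled scan. Restore confirmed responders for time to response and duration of response. State the ORR numerator and denominator.
- Show the unconfirmed per-visit rate as a labelled secondary line.
- If the sponsor prefers unconfirmed response as the main rate, label it so, report the confirmed rate beside it, and record the departure and its reason in SAP 13.
- Reconcile the Table 16 note with Protocol 12.2.2. The table's rows need no rewrite for the SAP, because SAP 9 does not use iRECIST best response.

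**Cost.** The fix needs SAP wording and one derivation, using scans already scheduled at week 12 and every 9 weeks thereafter (SAP 4.4). The drawback is real. The second scan falls at about week 12 + 9 = 21, and entry requires a life expectancy of only 8 weeks or more. Tumors with one post-baseline scan cannot be confirmed, so confirmed rates may fall by more than a little. Reporting how many tumors had no second scan, with both rates side by side, lets the reader judge how much of the drop comes from missing scans.

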9. EFFICACY ANALYSES

Due to the method of action of the INT230-6 therapy observed over the course of the study, proper assessment utilizing RECIST or iRECIST was not possible. A response across all lesions using sum of diameters to assess efficacy over time using response criteria was not utilized. Thus, efficacy analyses will largely focus on the response of individual tumors (injected and bystander) as opposed to an overall tumor response, and any overall response will utilize the modified response criteria defined below.

Efficacy analyses will be conducted on the All Treated Population (ATP), the Response Evaluable Population (REP), and the Scan Evaluable Population (SEP). RECIST 1.1 assessments were not collected. Rather injected tumor response and non-injected tumor response utilizing some of the RECIST criteria were evaluated. Sponsor utilized RECIST principles with the injected and non-injected tumor measurements obtained. Efficacy will be determined based on a modified version of RECIST 1.1 criteria. Specifically, complete response (CR) and partial response (PR) will be defined for injected tumors followed per RECIST 1.1 utilizing target lesions. Progressive disease will be determined by clinical or radiological deterioration leading to the subject being taken off-treatment at the discretion of the investigator. Stable disease (SD) is defined as any adequate assessment not considered CR, PR, or progression. The appearance of a new lesion will not necessarily be considered progression and if possible will be assessed. Any post-baseline visit where a target lesion present at baseline was not assessed will result in a Not Evaluable (NE) assessment for that lesion. Data will be presented by treatment and, when indicated, by subgroups.

The primary efficacy parameter is the disease control rate (DCR), defined as the number of subjects obtaining a best overall response of either CR, PR, or SD as described above divided by the total number of subjects in the analysis population. The DCR will be presented with accompanying 95% exact binomial confidence intervals for each study part for the ATP population, REP, SEP, and by subgroup.

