At baseline, lesions are classified as measurable or nonmeasurable per either RECIST 1.1 guidelines, depending on the cohort. Baseline measurable lesions are further classified as target (injected) or bystander (non-injected), while non-measurable lesions are classified as non-target (non-target lesions are not eligible for injection). A sum of diameters (SOD) (longest for extranodal lesions and shortest for lymph nodes) will be calculated for all target lesions. Tumor volume (for target tumors with three dimensions) will also be calculated using the modified

ellipsoid method or by longest diameter if specified in an particular protocol amendment. Bystander lesions will be recategorized as target lesions once injected, but target lesions will always remain target lesions.

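### SAP 9.1 puts a plain Clopper-Pearson interval on a tumor-level response rate with no allowance for several tumors per subject, and its counting rule must be reconciled

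*SAP*

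**What the plan says.** The unit of analysis is the tumor. SAP 9.1: "The ITR is defined as the ratio of CR + PR in injected tumors / total number of injected tumors". Appendix 1, item 3, likewise counts responding target tumors at a visit and divides by the target tumors at that visit. The estimator is the simple proportion, and for its precision: "The estimate of ITR will be accompanied by 2-sided 95% exact binomial confidence intervals as determined by the Clopper-Pearson method". ITR is among the parameters of which SAP 9.1 says "These endpoints will be summarized by treatment".

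Several injected tumors per subject are expected. Protocol 12.2.1 follows up to 10 target tumors. Protocol 5.2.1 spreads the EC3 dose over every tumor that can practicably be injected, and the SAP synopsis gives DEC2 and FEC the same INT230-6 regimen. SAP 7.5 foresees subgroups with fewer than 2, and with 2 or more, injected tumors. Neither document mentions clustering, a design effect, robust variance or a one-tumor-per-subject rule.

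On bystander tumors injected later, SAP 9.1 has three sentences:
- "tumors that become target during the study will also be included in the ITR calculation at the time they are treated"
- "Thus, bystander or non-target lesions dosed at later dates are not included in calculations for ITR"
- "Note that bystander tumors that are injected on study will be included in the ITR calculation"

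SAP 9 adds: "Bystander lesions will be recategorized as target lesions once injected". Table 2 puts injected and bystander rates for the monotherapy cohorts outside the SAP. SAP 13 reports no changes from the protocol's methods.

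**The concern.** Tumors in one subject share host, histology, any systemic checkpoint drug and probably the reader, so their responses are likely to be alike. A binomial interval on pooled tumors then treats correlated observations as independent and claims more precision than the data hold. SAP 9 gives up RECIST and iRECIST as a workable assessment and turns mainly to individual tumors. ITR is a secondary endpoint for DEC, DEC2 and FEC in Table 2, so its interval will be read as evidence of activity.

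The rate itself also needs one definition. The middle sentence in SAP 9.1 conflicts on its face with its neighbours, and the protocol gives two different bases for ITR.

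**Working it through.** **1. Inputs.** From the documents: tumor-level proportion, 95% two-sided Clopper-Pearson (SAP 9.1); at most 10 target tumors (Protocol 12.2.1); groups of up to 15 and a total of 45 subjects in FEC (SAP 4.1.2). Not given, so assumed: ICC 0.1, 0.2 or 0.4; true ITR 30%; tumors per subject. As a rough anchor, Protocol 5.2 mentions more than 200 tumors, Protocol 9.2 the first 70 patients and SAP 5 a total of 110 subjects: 200/110 = 1.8 and 200/70 = 2.9. The dates differ, so this only suggests a mean of about 2 to 3.

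**2. Check of the routine.** The plan states no figure for ITR. Exact 90% limits for 16 subjects with 3, 4 and 5 responses are 5.31-41.66%, 9.03-48.44% and 13.21-54.83%, which match SAP 5.

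**3. Design effect.** With equal counts m, DE = 1 + (m - 1) x ICC. With variable counts, DE = 1 + (E[m²]/E[m] - 1) x ICC. For m = 1 + Poisson(2), E[m] = 3 and E[m²] = 11, so DE = 1 + 2.667 x ICC = 1.27, 1.53 and 2.07 at ICC 0.1, 0.2 and 0.4.

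**4. One worked interval.** Take 50 subjects with 3 tumors each and 45/150 responding (30%). The planned method gives 22.8-38.0% (15.2 points). At ICC 0.3, DE = 1.6 and effective n = 150/1.6 = 93.8, giving 21.0-40.3%. At ICC 0.5, DE = 2.0 and effective n = 75, giving 20.0-41.7% (21.7 points).

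**5. Coverage of the planned interval** (beta-binomial simulation, true ITR 30%, 15 to 45 subjects, variable counts 1 + Poisson capped at 10):

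| Mean tumors | ICC 0.1 | ICC 0.2 | ICC 0.4 |
|---|---|---|---|
| 2 | 95-96% | 93-94% | 90-91% |
| 3 | 93-94% | 90-92% | 85-86% |

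At mean 3 with 15 subjects, a design-effect-adjusted interval averages 31.9 points against 27.9 at ICC 0.1 (14% wider) and 39.1 against 27.7 at ICC 0.4 (41% wider). Its coverage was 94.6-97.2% with 15 or 45 subjects and 92.3-99.4% with 6, over fixed and variable counts with means 2, 3 and 5. All runs draw tumor number independently of response.

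**6. Low counts.** A variance-based adjustment fails when few subjects respond. Take 15 subjects with 3 tumors each.
- 0/45: the design effect is undefined. Using the 15 subjects as effective n gives an upper limit of 1 - 0.025^(1/15) = 21.8%.
- 1/45: the residuals are 14/15 once and -1/15 fourteen times, with squares summing to 210/225. Multiplying by K/(K - 1) = 15/14 gives 1.0. The robust variance is 1/45² and the binomial variance is (1/45)(44/45)/45, so DE = 45/44 = 1.02 and the upper limit is 11.9%.

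One response would lower the upper limit from 21.8% to 11.9%. With 6 subjects of 3 tumors it falls from 45.9% (0/18) to 28.2% (1/18).

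**7. Counting rule, passages side by side.**
- SAP 9.1, first and third sentences quoted above: later-injected bystanders count. Second sentence: lesions dosed later do not.
- SAP 9 and Appendix 1, items 3 and 4: an injected bystander becomes a target and counts from its injection visit, so the denominator changes by visit. The example under Other Notes agrees, and SAP 7.1 sends programmers to this appendix.
- Protocol 12.2.1: later-injected bystanders and injected new measurable lesions may count.
- Protocol 12.2.2: confirmed responses over tumors identified at baseline. The SAP requires neither.

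**The case against.** The interval is descriptive; no test or decision rule uses it. At means of 2 to 3 tumors and ICC 0.1 to 0.2, coverage stays at 90-96%; a clear loss needs an ICC near 0.4, which nothing in the documents supports. Subjects with a single injected tumor limit the loss further. All of this stands, and it limits the weight of the point. It does not justify an independence assumption that the design contradicts.

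The simulations have their own limit. Under Protocol 5.5 the physician weighs the response of injected tumors when choosing what to inject next, so tumor number may depend on response. Coverage in that situation is untested.

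A reader might infer that SAP 9.1 leaves ITR undetermined and that the reported rate could move by several points. If the excluding sentence were programmed, the shift would be the share of tumors injected later times the gap in response rate. Assumed shares of 10-30% and gaps of 10-30 points give 1 to 9 points. The documents do not support expecting this: the sentence can be read by visit (lesions dosed later are not yet counted), and Appendix 1 gives that rule explicitly.

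A reader might also infer that the sentence can simply be deleted, because SAP 9 makes non-target lesions ineligible for injection. That is unsafe. Protocol 5.5 allows injection of superficial lesions, including nodes, from 1.0 cm, while Protocol 18.1.3 asks for 15 mm in short axis for nodal lesions. An injected non-measurable lesion is foreseeable and needs a stated rule.

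**Conclusion.** The point holds. SAP 9.1 attaches an interval for independent units to a tumor-level rate and makes no allowance for correlation within a subject. If that correlation is positive, the interval is too narrow. As an illustration, under the assumptions above, nominal 95% coverage is about 93-96% at ICC 0.1, 90-94% at 0.2 and 85-91% at 0.4. The true loss cannot be fixed from the documents, and with 2 tumors per subject and a low ICC there is little or none.

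A reader might take this to undermine the trial's main efficacy result. It does not: the disease control rate is counted per subject. What is affected is the stated precision of a secondary endpoint in DEC, DEC2 and FEC, and of monotherapy ITR if it is reported under this SAP. The wording conflict in SAP 9.1 is real but largely resolved by Appendix 1. The differences from Protocol 12.2.2 are not recorded in SAP 13. This should be corrected, but it does not threaten the trial's conclusions.

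**What to change.** 1. **Interval.** Replace the plain interval with one that treats the subject as the cluster: a design-effect-adjusted Clopper-Pearson, a GEE with robust variance, or a subject-level bootstrap. Pre-specify one. For no or few responding subjects, set a single rule under which the upper limit never falls when a response is observed, for example the number of subjects as effective n for every low count and not only for zero. Check the count at which that rule hands over to the usual method. At each timepoint report the number of subjects and tumors per subject, and the subject-level proportion with any injected-tumor CR or PR with its exact interval.
2. **Wording.** Reword the excluding sentence in SAP 9.1 to match SAP 9 and Appendix 1, items 3 and 4: a bystander counts from the visit at which it is injected, not before. State how an injected non-measurable lesion and an injected new lesion are handled.
3. **Protocol.** Reconcile the SAP with Protocol 12.2.1 and 12.2.2 on denominator, new lesions and confirmation of response, and record any departure in SAP 13.
4. **Table 2.** Reconcile it with SAP 9.1 on whether monotherapy ITR is reported under this SAP.

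The cost is SAP wording, any entry needed in SAP 13 and a few lines of code. The downsides are wider intervals, coverage that is not assured in very small groups, and a subject-level proportion that answers a different question because it rises with the number of tumors injected.
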